² If the participant tests positive for SARS-CoV-2, he/she is not enrolled in the study. The investigator's approach should be in compliance with the current version of the guidelines "Prevention, diagnosis and treatment of a new coronavirus infection (COVID-19) by the Ministry of Health of the Russian Federation.

³ Contraindications for the second dose of the vaccine: Severe post-vaccination adverse events (anaphylaxis, severe generalized allergic reactions, convulsive disorder, fever (\geq 40°C), etc.) following the injection of the first dose of the vaccine.

If a laboratory-confirmed case of SARS-CoV-2 infection (with or without symptoms) is detected, the participant prematurely completes the study as having reached the primary endpoint.

If the PCR test for SARS-CoV-2 is positive, in accordance with the requirements of Rospotrebnadzor, the information is transferred to the health care facility to which the participant is attached, where he will be provided with the necessary medical care (according to current standards). Health care facility employees report data on COVID-19 cases (in accordance with the recommendations of the Ministry of Health of the Russian Federation and the rules of health care facilities).

Possible post-vaccination symptoms;

- general (flu-like syndrome characterized by chills, fever, arthralgia, myalgia, asthenia, malaise, headache) and local (pain at the injection site, hyperemia, swelling) symptoms that develop on the first-second day and resolve within three days;
- nausea, dyspeptic disorder, loss of appetite;
- enlarged regional lymph nodes;
- allergic reactions;
- transient increase in serum levels of liver transaminases, creatinine, and creatine phosphokinase.

These post-vaccination symptoms are not recorded as adverse events (either associated with the study product administration or developing after discontinuation); they are registered by the participant in a diary and assessed by the physician as post-vaccination complications.

Transient flu-like syndrome should not be diagnosed as ARVI, in this case a PCR test for SARS-CoV-2 is not carried out.

If the participant develops COVID-19 or is hospitalized for COVID-19, then delayed telephone visit will be performed. The duration of the visit is determined by the study investigator on a case-by-case basis.

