- 11. Patient belongs to the study site personnel directly involved in the study or is the closest relative of the study investigator. "Immediate relative" means husband, wife, parent, son, daughter, brother, or sister (regardless of whether they are natural or adopted).
- 12. Patient who works for OOO "NPF "MATERIA MEDICA HOLDING" (i.e. i.e. they are employees of the Company, temporary employees on a contract basis or appointed officials responsible for conduction of the study or their immediate family members).

Criteria for Withdrawal or Termination

- 1. Screening failure.
- 2. Laboratory-confirmed case of SARS-CoV-2 infection (with or without symptoms).
- 3. Inability or refusal of the patients to comply with the protocol requirements.
- 4. Use of any medication listed in the section "Prohibited concomitant medications".
- 5. An adverse event requiring discontinuation of the study.
- 6. Participant's decision to complete the study early due to lack of the therapy efficacy or any other reasons.
- 7. Pregnancy.
- 8. Cases not specified by the protocol when, according to the investigator's opinion, further participation in the study harms the patient.
- 9. Eligibility error.
- 10. Participation in any other clinical trial.
- 11. Unblinding.

Number of subjects

Study stage before adaptation:

1268 participants will sign the informed consent.

At least 1206 participants will be randomized.

Study stage after adaptation⁴:

Additional 0 to 2332 participants will sign the informed consent.

Therefore, additional 0 to at least 2214 participants will be randomized.

The total maximum sample size will be: 3600 participants will sign the ICF, n=**3420** of which will be randomized.

⁴ Refer to the section Statistical Methods

Interim analysis

An "unblinded" interim analysis for 85% of the sample (0.85 information, 485 PP participants each) is planned in the protocol. It is assumed that the study can be stopped due to the rejection of the null hypothesis with the O'Brien-Fleming type I error spending function. Based on the results of this analysis (if the stopping parameters are not achieved), it is assumed that the study will be adapted to determine the required additional sample size.

Treatment

Group 1

Name of the medicinal product: Ergoferon

Active ingredient: affinity purified antibodies to human gamma interferon – 0.006 g*

affinity purified antibodies to histamine - 0.006 g*

affinity purified antibodies to CD4 - 0.006 g*

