 - drug products with thymus hormones;
 - herbal immunostimulants (immunal®, etc.).
- 3. Immunosuppressants (L04).
- 4. Antitumor drugs (L01) and antitumor hormonal drugs (L02).
- 5. Immune sera and immunoglobulins (J06).
- 6. Vaccines (J07).
- 7. Corticosteroids for systemic use (H02AB).
- 8. Any unapproved medicinal product.
- 9. Drugs that previously caused hypersensitivity/allergic reactions in patient.

Study design scheme

Schedule of study procedures

Procedure/ Visit	Visit 1 (Day 1)	Visit 2 (Day 22 + 3 days)	Unscheduled visit [*]	Visit 3 «phone» ▲ (Day 35 + 3 days)
Informed consent	+			
Registration in the IVRS and assignment of a personal code	+			
Rapid test for SARS-CoV-2 (COVID-19 Ag)	+	+		
Demographics	+			
Medical history	+			
Concomitant diseases and conditions	+	+	+	+
Concomitant therapy	+	+	+	+
Nasopharyngeal and oropharyngeal (throat) swabs for PCR diagnostics	+*	+*	+	
Pregnancy test	+			
Inclusion/exclusion criteria	+			
Randomization and prescription of study therapy	+			
E-diary supply	+	+	+	+
Study drug supply	+			

				17 0001 202	
Study drug accountability,		1			
compliance assessment		Т			
Evaluation of treatment safety	+	+	+	+	
Visit completion	+	+	+	+	
Study completion [•]					
* Conducted in case of a participant's illness with COVID-19					
▲ If the participant has had COVID-19	or has been hosp	italized for COVII	D-19, the timing of	the visit is	
determined by the study investigator of	n a case-by-case b	asis.			
	C GING G H A				

* Conducted with a positive rapid test for SARS-CoV-2 (COVID-19 Ag).

◆ If a patient falls ill with COVID-19, he or she will terminate participation in the study early.

Statistical Analyses

Samples

Total set: All subjects who signed Informed Consent Form (ICF). This sample will consider all adverse events (AEs) throughout the study, including those occurred prior to the study therapy.

The sample including all enrolled and randomized patients who received at least one dose of the study drug to be used for *analysis of the study treatment safety and tolerability* (*Safety population*), as all AEs identified after the study drug administration will be recorded.

The AEs registered in patients of the *Total set* sample from the moment of signing the Informed Consent Form, but before the test drug administration will not be taken into account when analyzing the study therapy safety.

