Full Analysis Set. This sample includes all the enrolled patients, except for those who have experienced at least one of the following events:

- 1) non-compliance with inclusion/exclusion criteria;
- 2) patient did not take any dose of study drug;
- 3) absence of any patient data after administration of study drug.

Patients who had at least one of the listed events may be excluded from the analysis.

This sample, the most consistent with the "Intention-to-treat" principle, will be used for the *Intention-to-treat analysis (ITT analysis)* of the the study therapy efficacy.

Per protocol set. This sample includes all the patients who received full protocol therapy, completed all the scheduled visits. This sample will be used for *Per Protocol analysis (PP-analysis) of the the study therapy efficacy. Per Protocol set* will not include the patients whose data are fully or partially invalid for analysis due to a protocol deviation.

Protocol deviations resulting in full or partial data invalidity:

- 1. Violation of visit schedule.
- 2. Inappropriate distribution/issue of the study drug.
- 3. Prescription of prohibited therapy.

- 4. Increase or decrease of 25% or more in the amount of study therapy received.
- 5. Inability to assess patient's objective compliance (adherence to therapy) according to the formula (e.g. loss of packaging).
- 6. Major discrepancies between source documents and CRF detected during monitoring or other authorized inspection.
- 7. Violations of the Informed consent procedure.
- 8. Non-compliance with the clinical study protocol procedures.
- Inability to collect all patient's data used for evaluation of the study endpoints (e.g. lack of entries in source documents required for verification of inclusion/exclusion criteria, safety and efficacy criteria).
- 10. Any other protocol deviations that fall under definition of "significant deviation."

Data treatment and all statistical calculations under the protocol will be made using SAS-9.4 statistical software.⁵

Evaluation of sample size

The sample size has been assessed on the basis of the following rules and assumptions:

- 1. Statistical provisions.
 - 1.1 the power of the statistical tests " $P = (1 \beta)$ " is assumed to be 80% (the probability of correct rejection of the null hypothesis is 0.8);
 - 1.2 the probability of a type I error " α " is allowed to be less than 5% (the probability of the erroneous acceptance of an alternative hypothesis is less than 0.05);

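### Read literally, the per-protocol definition drops infections confirmed before Visit 2 from the set on which the trial is sized, and no set is named for the final test

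*Combined protocol and SAP*

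**What the plan says.** - **PP set** (Statistical Analyses, Samples): "This sample includes all the patients who received full protocol therapy, completed all the scheduled visits". The deviations listed below it include violation of the visit schedule (1), "Increase or decrease of 25% or more in the amount of study therapy received" (4), inability to assess compliance (5) and departure from protocol procedures (8). Neither the definition nor the list treats endpoint cases separately.
- **What happens to a case** (Study design): on laboratory confirmation "the participant prematurely completes the study as having reached the primary endpoint". The same event is item 2 of the withdrawal criteria. A footnote to the Schedule of study procedures adds: "If a patient falls ill with COVID-19, he or she will terminate participation in the study early".
- **Follow-up of a case** (Study design): "If the participant develops COVID-19 or is hospitalized for COVID-19, then delayed telephone visit will be performed".
- **Timing**: three weeks of therapy to Visit 2 on Day 22, within five weeks of observation.
- **Sizing** (Evaluation of sample size): 570 per group, labelled as the PP sample, from 3% versus 0.5%. N_PP is described as the planned number who finish per protocol.
- **Interim analysis**: "0.85 information, 485 PP participants each) is planned in the protocol".
- **FAS** (Samples): used for the intention-to-treat analysis of efficacy. Its exclusions are ineligibility, no dose taken and no data after dosing: "Patients who had at least one of the listed events may be excluded from the analysis". None of them depends on early termination.
- **Final test** (Sample Size Adaptation, item 7): the critical value 2.0255 is fixed, but no analysis set is named.

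**The concern.** The event that the trial counts is also the event that stops a participant from meeting the PP definition. Someone confirmed positive before Day 22 has had less than three weeks of therapy and does not reach Visit 2. A programmer who applies the definition as written would remove that participant, and the event would go too.

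The trial expects few events, about 17 on placebo and 3 on Ergoferon, so each lost case matters. If PP is the deciding set, power falls, and the interim statistic is more likely to land in the pessimistic zone, where the sample size is not increased. Separately, the interim is unblinded while the choice between FAS and PP for the final test is left open.

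**Working it through.** **1. Reproduce the planned size.** Inputs from Evaluation of sample size: p0 = 0.03, p1 = 0.005, two-sided alpha 0.05, power 80%, O'Brien-Fleming boundaries with looks at 0.85 and 1.

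- Classical O'Brien-Fleming boundaries are 2.197 and 2.0255. The second equals the plan's final critical value. The drift for 80% power is 2.828.
- Odds ratio = (0.005/0.995)/(0.03/0.97) = 0.1625; ln(OR)² = 3.302.
- V = 1/(0.03 × 0.97) + 1/(0.005 × 0.995) = 235.37.
- n = drift² × V / ln(OR)² = 7.997 × 235.37 / 3.302 = 569.98, so **570 per group**, as stated.

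**2. Who is lost on the literal reading.**

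| Confirmation | Full therapy | All visits | In PP as written |
|---|---|---|---|
| Before Visit 2 | No | Visit 2 missing | No |
| At or after Visit 2 | Yes, if compliant | Visit 3 depends on whether the delayed telephone visit counts | Unclear |

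**3. Effect on the odds ratio.** Let L be the fraction of cases removed. The rate within PP becomes p(1 − L)/(1 − pL), so the odds become (1 − L) × p/(1 − p). With the same L in both arms, (1 − L) cancels and the odds ratio stays at 0.1625. With unequal loss it is multiplied by (1 − L_Ergoferon)/(1 − L_placebo). Two illustrations with no basis in the documents: 50% lost on placebo and 40% on Ergoferon gives 0.195; 40% and 50% gives 0.135.

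**4. Effect on power.** The documents give no case timing, so L is assumed. Constant risk gives 21/35 = 60%; 20% and 40% are shown as lower values. It is also assumed that 3% is the rate over all cases. With 570 PP members per arm, drift = √(570/V_L) × |ln OR|, where V_L is V at the reduced rates:

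| L | PP rates | Expected PP cases per arm | Drift | Power | n per arm for 80% |
|---|---|---|---|---|---|
| 0% | 3.00% v 0.50% | 17.1 v 2.9 | 2.828 | 80% | 570 |
| 20% | 2.41% v 0.40% | 13.8 v 2.3 | 2.534 | 71% | 711 |
| 40% | 1.82% v 0.30% | 10.4 v 1.7 | 2.198 | 59% | 944 |
| 60% | 1.22% v 0.20% | 7.0 v 1.1 | 1.798 | 43% | 1411 |

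**5. Sensitivity to the test.** The log odds ratio basis is conservative here. Exact two-stage enumeration used 485 then 570 per arm, chi-square or Fisher by cell count, and rates p(1 − L):

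| L | Exact power, no increase | Exact power, planned increase | P(Z1 < 1.6815), no increase allowed |
|---|---|---|---|
| 0% | 90% | 93% | 9% |
| 20% | 80% | 84% | 18% |
| 40% | 64% | 68% | 34% |
| 60% | 40% | 43% | 58% |

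Using the conditional rates of step 4 at 60% loss gives 41% and 45% instead of 40% and 43%. On this scale the 80% target survives a loss of about 20% without the increase, or 26% with it.

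**6. Do the adaptation cut-offs identify the set?** Dividing the conditional power formula through by √N_min, with r = N1/N_min, its argument is (2.0255 − Z1√r)/√(1 − r) − Z1√((1 − r)/r). Only r enters. At 485/570, conditional power is 0.300 at Z1 = 1.6815 and 0.800 at 2.168. At 513/603 (85% of the randomized number per arm) the results are the same to three decimals. The cut-offs cannot tell PP from FAS.

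**The case against.** **The wording may intend to keep cases.** A confirmed case is said to complete the study, N_PP is described in terms of completing, and cases get a delayed telephone visit. This is a fair reading and may be what the sponsor means. But the PP definition does not say so, and the withdrawal criteria class the same event as termination.

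**The FAS keeps early cases.** This stands. The trial has an efficacy set that counts them, so harm needs two further steps: the literal reading is applied, and PP decides the result.

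**The text supplied is a protocol summary.** This also stands. It mentions a compliance formula that it does not give, and a fuller protocol may name the primary set.

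**Constant risk may overstate the loss.** This stands too. After entry, symptom-free infections are sought only at Visit 2, and transient post-vaccination flu-like syndrome is not PCR-tested. Entry also requires a negative rapid test and no infectious symptoms. The 60% figure may therefore be too high.

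**The dropout allowance covers it.** This does not stand. The 10% allowance replaces participants. Selective removal of cases leaves 570 PP members carrying fewer events than 3% versus 0.5% implies.

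**A reader might infer that the cut-offs prove that Z1 is computed on PP.** They do not, because they depend only on the 0.85 ratio. The case for PP at the interim rests on the stated count of 485 PP participants and on the 570 being a PP number.

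**Conclusion.** The concern holds as a defect of wording that can cost power. As written, the PP definition excludes infections confirmed before Visit 2, and the set for the final test is not named in the text supplied. If PP decides and 20%, 40% or 60% of cases are lost, power on the plan's basis is 71%, 59% or 43% instead of 80%. These figures rest on literal application, on PP being the deciding set, on an assumed case timing, and on 3% being the rate over all cases. They are illustrations, not a forecast.

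Two stronger readings are not supported. A reader might infer that the result will be biased, perhaps towards Ergoferon, because more placebo than Ergoferon cases are removed. Equal fractional loss leaves the odds ratio unchanged, and the documents give no ground for unequal fractions or for a direction. A reader might also infer that the final test will be run on PP; the text does not say which set it uses.

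This should be fixed, but it does not invalidate the trial. Confidence is medium.

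**What to change.** Before the interim is unblinded:

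1. **PP definition.** State that a participant with a PCR-confirmed case stays in the PP set if compliant up to the date of the positive PCR, with visits and therapy judged only to that date. State also that visits, therapy or drug accountability not completed because of the endpoint do not count as deviations 1, 4, 5 or 8. The second sentence is needed: drug accountability appears to be scheduled at Visit 2, so an early case could otherwise still be excluded because compliance cannot be assessed.
2. **Deciding set.** Name one set for Z1, conditional power and the final primary test, preferably the FAS, with PP supportive. If the FAS is named, restate N1 and N_min as FAS counts; the cut-offs do not change at the same 0.85 ratio.
3. **Later cases.** Reconcile the early-termination footnote in the Schedule of study procedures with the delayed telephone visit, so that it is clear whether Visit 3 counts as completed for cases at or after Visit 2.

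The cost is protocol and SAP wording, with no added participants. The effect seen in the FAS may be slightly smaller than in an idealised PP set.

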 - 1.3 statistical criteria of intergroup comparisons will be two-sided unless otherwise specified;
 - 1.4 ratio between Ergoferon and Placebo sample sizes is 1:1 (1 Ergoferon patient per 1 Placebo patient);
 - 1.5 an "unblinded" interim analysis with possibility of early stopping due to the effectiveness on 85% of the sample is planned in the protocol. Error spending function O'Brien-Fleming;
 - 1.6 sample size can be adjusted after the interim analysis based on the estimated conditional power (at the same time as the interim analysis is conducted);
 - 1.7 statistical null and alternative hypotheses regarding the superiority of Ergoferon over Placebo for the dosing regimen used:

Primary endpoint:

H₀: $OR_{12} = 1$

⁵ Holder of license: OOO "NPF "Materia Medica Holding", No. 70100045.

Ha: OR1 $2 \neq 1$

where OR_{12} – odds ratio of an event occurring between the Placebo and Ergoferon.

The following SAS code was used to determine the required sample size⁶:

proc seqdesign errspend;

design nstages = 2 info = cum (0.85 1) method (alpha) = obf alt = twosided stop = reject alpha = 0.05 beta = 0.2 samplesize model = twosamplefreq (nullprop= $0.03 \text{ prop}=0.005^7$)

run

1.8 the final sample size is calculated with the following formula:

$$\mathbf{N} = \mathbf{N}_{PP} / (1 - \mathbf{K}_{B}),$$

where N – final sample size; N_{PP} – sample size value in c. 1.7, i.e. scheduled number of patients completing the study per protocol; K_B – withdrawal rate.

2. Assumptions about the expected effects of the clinical study:

It is assumed that the **odds ratio** for the occurrence of an event will be not less than 0.162 in favor⁸ of Ergoferon (as part of the adaptation process, a possible deterioration in the magnitude of the prediction of the effect is assumed to be up to 0.55).

Population frequency: assumed to be 3%⁹.

Therefore, the required size for each group is 570^{10} patients (PP sample). Considering the potential dropout of about 10% patients during the study for various reasons¹¹, at least 1268 patients (634 in each group) will be required to sign informed consent, of which 1206 patients will be randomized (603 in each group) (see cl. 1.8, the final total withdrawal rate will be ($K_B = 0.1$).

⁶ Minimum size for this study.

⁷ Equivalent to effect size OR=0.162 (smaller is better).

 $^{{}^{8}}$ OR = Odd_{tr}/Odd_{pl} – the higher, the greater the chance in Ergoferon group compared to the Placebo group.

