 ⁹ Rare event frequency assessment, is a population parameter and can be overestimated in a blinded interim analysis.
 ¹⁰ Minimum size.

¹¹ Of them patients dropped out during the screening process (5%)

Sample Size Adaptation

It is intended to adapt the sample size during the study in accordance with the following algorithm¹²:

 During the planned interim analysis (if the study was not completed due to rejection of the null hypothesis based on the interim analysis cutoff), the conditional power is calculated using the formula:

$$CPower = 1 - \Phi\left(\frac{z_{\alpha} * \sqrt{N_{min}} - z_{1} * \sqrt{N_{1}}}{\sqrt{N_{min} - N_{1}}} - \frac{z_{1} * \sqrt{N_{min} - N_{1}}}{\sqrt{N_{1}}}\right)$$

where Z_1 is the value of the Z-statistic obtained at the interim analysis on N_1 of the first patients from N_{min} (the minimum sample size of the study);

Za = 2.0255 (the value of statistics for the final analysis, taking into account the presence of an interim analysis);

- $\Phi_{(x)}$ the probability value of event **X** for the standard normal distribution ($\sigma = 1, \mu = 0$).
- 2) The maximum allowable increase in sample size is assumed to be no more than 3240^{13} .
- 3) Taking into account the above, one of the adaptation scenarios will be selected.
- 4) Optimistic scenario (conditional power CPower > 0.8, or equivalently Z₁ > 2.168): sample size does not change (N_{final} = N_{min}).
- 5) Medium scenario (conditional power 0.3¹⁴ < CPower < 0.8, or equivalently value 1.6815 < Z1 < 2.168): the sample size changes according to the formula:

$$N_{final} = N_1 + \left(\frac{N_1}{z_1^2}\right) * \left(\frac{z_{\alpha} * \sqrt{N_{min}} - z_1 * \sqrt{N_1}}{\sqrt{N_{min} - N_1}} + z_{\beta}\right)^2$$

- 6) Pessimistic scenario (conditional power CPower < 0.3, or, equivalently, value Z1 < 1.6815): sample size does not change (N_{final} = N_{min}).
- 7) The final statistical analysis is carried out with the critical statistical values obtained by estimating the minimum sample size ($Z\alpha = 2.0255$).

Statistical criteria

All the statistical calculations will be performed using two groups of statistical criteria:

¹² Adaptive Increase in Sample Size when Interim Results are Promising: A Practical Guide with Examples Cyrus R. Mehta1,2, Stuart J. Pocock3 STATISTICS IN MEDICINE Statist. Med. 2000; 00:1–6

¹³ Taking into account withdrawal - up to 3600

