- 2. For the frequency analysis of 2×2 cross tables $-\chi^2$ -test (if the compared frequencies are greater than 5) or Fisher exact test (if one of the compared frequencies is less than 5).

- 3. For the frequency analysis of cross tables with independent strata Cochran–Mantel– Haenszel test (modification of the χ^2 -test for multiple comparisons).
- 4. For the frequency analysis of data on the presence / absence of an event or outcome during repeated measures (cross tables with dependent strata) survival analysis.

To perform the above-mentioned non-parametric statistical analysis options, it is assumed that the following SAS procedures are used:

- FREQ Friedman test, χ^2 -test and / or Fisher exact test; Cochran–Mantel–Haenszel test
- LIFETEST survival analysis
- NPAR1WAY Mann-Whitney U-test.

Safety parameters

Adverse events recorded during the study will be grouped into frequency tables by severity, seriousness and relationship with the study drug.

Data presentation

Descriptive statistics will be provided for each study continuous / interval variable. Numerical data will be presented by mean, standard deviation, min and max values, as well as 1st, 2nd and 3rd quartiles (other measures of central tendency and dispersion may be additionally provided if necessary). The categorical variables will be presented as frequency tables by visits. Comparisons suggesting statistical conclusion will have the relevant confidence intervals. Outliers will be analyzed individually. The data will be grouped by visits.

Incomplete/missing data

Missing data not requiring the patient exclusion from analysis will be processed as follows:

- 1. For sections of descriptive statistics the missing/incomplete data will be ignored specifying the number of complete and incomplete data points.
- 2. For efficacy criteria, if the type of gaps (MCAR, MAR, etc.) and the type of variable are acceptable, **multiple imputation** methods can be applied. Alternative methods: data will be populated according to the **LOCF** approach.
- 3. For additional criteria similar to descriptive statistics.

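### The chi-square/Fisher switch should be keyed to expected rather than compared counts, and the plan should name the test used for the primary endpoint at both looks

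*Combined protocol and SAP*

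**What the plan says.** Under Statistical criteria, Non-parametric criteria, item 2 covers 2×2 tables. The chi-square test applies "if the compared frequencies are greater than 5) or Fisher exact test (if one of the compared frequencies is less than 5". The words observed and expected do not appear, and a frequency equal to 5 falls in neither branch.

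The primary endpoint compares the number of laboratory-confirmed infections in two groups. Evaluation of sample size states its null hypothesis as an odds ratio of 1, but no test is named for it there or elsewhere. The sizing assumptions are "Population frequency: assumed to be 3"% and a footnoted effect "Equivalent to effect size OR=0.162 (smaller is better"). The design statement is "info = cum (0.85 1) method (alpha) = obf alt = twosided stop = reject alpha = 0.05 beta = 0.2".

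Sample Size Adaptation takes an interim Z-statistic as input. Its item 7 adds: "The final statistical analysis is carried out with the critical statistical values obtained by estimating the minimum sample size", with the value 2.0255.

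**The concern.** The usual condition for the chi-square approximation concerns the expected counts under the null: the pooled event rate times the arm size. With 1:1 arms, the expected number of cases per arm is half the total. The count in the better arm is not a validity criterion. It is low when the drug works.

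A switch on observed counts therefore sends the tables that show a benefit to the more conservative test. At stake are some power, a larger share of the chance of stopping at the interim, and the conclusion for a few borderline tables. A result with exactly 5 cases in one arm would leave the choice of test open until the data are seen.

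The adaptation adds a difficulty. Its formulas need a Z value, and Fisher's test gives only a p-value.

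**Working it through.** **Inputs.** From Evaluation of sample size: event rates 0.03 and 0.005, 570 per arm per protocol, two-sided alpha 0.05, power 80%. From Interim analysis: 485 per arm. From Sample Size Adaptation: final critical value 2.0255.

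**1. The plan's own figures.** A two-stage, two-sided O'Brien-Fleming design at information 0.85 and 1 has a final boundary of 2.0255, as stated. Its interim boundary, which the document does not print, is 2.0255/√0.85 = 2.197. The nominal two-sided p-values are 0.0428 and 0.0280. The drift for 80% power is 2.828. On the log-odds-ratio scale:

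- variance term: 1/(0.03×0.97) + 1/(0.005×0.995) = 235.37
- ln OR = ln[(0.005×0.97)/(0.995×0.03)] = ln 0.1625 = −1.817
- n = 2.828² × 235.37 / 1.817² ≈ 570 per arm (569.98 before rounding)

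The stated 570 is reproduced.

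**2. Which test is selected at 3% against 0.5%.**

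| | Interim, 485 per arm | Final, 570 per arm |
|---|---|---|
| Mean placebo cases | 485×0.03 = 14.55 | 570×0.03 = 17.1 |
| Mean Ergoferon cases | 485×0.005 = 2.425 | 570×0.005 = 2.85 |
| Expected cases per arm, pooled | (14.55+2.425)/2 = 8.49 | (17.1+2.85)/2 = 9.98 |
| P(Ergoferon count below 5), so Fisher as written | 90.1% | 84.0% |
| P(expected count below 5), i.e. total below 10 | 2.5% | 0.5% |

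The Ergoferon count is exactly 5 in 9.1% of final analyses.

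**3. Power.** All binomial tables were enumerated at both looks, without the sample-size increase, rejecting in the direction of benefit when p is at most 0.0280 (interim) or 0.0428 (final). A count of 5 was treated as chi-square.

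| Scenario | Rule as written | Expected-count rule |
|---|---|---|
| 3% vs 0.5%, stop at interim | 76.5% | 82.6% |
| 3% vs 0.5%, overall power | 90.3% | 92.5% |
| 3%, OR 0.55, overall power | 30.3% | 30.8% |

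At the final look alone, power is 89.9% against 92.0%, so the conclusion changes in about 2% of trials.

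**4. Type I error.** The one-sided two-look error of the expected-count rule is 2.48%, 2.37% and 1.81% at common rates of 3%, 1.75% and 1%. Its two-sided maximum over common rates of 0.2% to 4% is 4.97%. The switch on observed counts is not needed to stay within 5%.

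**5. Tables that change conclusion at the final look (cut-off 0.0428).** The first three are Fisher's under the rule as written; the last is unassigned. All have expected case counts of at least 5.

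| Placebo vs Ergoferon | Chi-square p | Fisher p |
|---|---|---|
| 9 vs 2 | 0.034 | 0.064 |
| 11 vs 3 | 0.031 | 0.056 |
| 13 vs 4 | 0.028 | 0.047 |
| 14 vs 5 | 0.037 | 0.061 |

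At the interim, 10 vs 2 has a Pearson Z of 2.32, above 2.197. Its Fisher p is 0.037, equivalent to Z = 2.08. That lies between 1.6815 and 2.168, the plan's medium scenario, in which the sample is enlarged.

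**The case against.** Several counter-arguments carry weight.

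- **The reading.** Observed is an inference. If the authors meant expected counts, the power loss disappears and only loose wording remains, with the gap at 5.
- **The scope.** Item 2 sits in a list of possible comparisons, and nothing assigns it to the primary endpoint. The interim is written on a Z-statistic, which a Fisher branch does not supply. Generalized linear models and survival analysis are also listed. This stands: every figure above is conditional on item 2 governing both looks. It also means that rewording item 2 is not enough unless the primary test is named.
- **The benchmark.** The 570 comes from a log-odds-ratio Wald calculation. That Wald test, with 0.5 added where an arm has no cases, has 90.2% power and a 74.6% chance of stopping at the interim, so the rule as written loses nothing against it. It also fails to reject for 9 vs 2 (Z 1.93), 11 vs 3 (2.01) and 14 vs 5 (1.99), and rejects for 13 vs 4 (2.08). This limits the weight of the example tables. It does not make the observed count a sound criterion.
- **The direction.** Moving to Fisher is conservative and does not create false successes. That is correct.
- **The adaptation.** The calculation leaves out the sample-size increase, so these are not the operating characteristics of the full plan.

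**Conclusion.** The point holds as a minor one. Item 2, read naturally, uses the wrong counts to choose the test and leaves a count of 5 open. If it governs both looks at 3% against 0.5%, without the sample-size increase, it costs 92.5 − 90.3 = 2.2 points of power and 82.6 − 76.5 = 6.1 points of interim stopping probability. It gives no needed protection of type I error in return.

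A reader might infer more, and the documents do not support it:

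- The 84% is how often Fisher's test is selected. It is not how often the conclusion changes, which is about 2% of trials at the final look.
- The trial is not left short of power by this rule. At the assumed effect, power stays near 90%, while the plan's target "is assumed to be 80% (the probability of correct rejection of the null hypothesis is 0.8").
- The loss is not general across effect sizes. At an odds ratio of 0.55, the weakest that the plan allows for, it is about 0.5 point.
- No effect on the hospitalisation comparison is shown. That endpoint is exploratory and no rate is given. With very few events, both rules would choose Fisher's test.

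**What to change.** Reword item 2 along these lines: *chi-square test without continuity correction if all expected cell counts (pooled rate times arm size) are 5 or more; Fisher exact test if any expected cell count is below 5.* This also settles the case of exactly 5.

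Add one sentence stating that this is the test for the primary endpoint at both the interim and the final analysis, and that its Pearson Z is the statistic used in the conditional-power and sample-size formulas and compared with the boundaries.

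The cost is two sentences in the statistical section, settled before the interim data are unblinded. No participants or procedures are added, and the two-sided type I error stays within 5% in the two-look calculation above.
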